Placebo-control reminder script (PCRS)		X ^l	X	X		X		X	
Structured Interview Guide for MADRS (SIGMA)		X ^l	X	X		X		X	
CGI-S		X ^l	X	X		X		X	
Participant Self-Rating Assessments									
SHAPS		X ^l						X	
PROMIS-Ability to Participate in Social Roles and Activities		X ^l	X	X	X	X	X	X	
PHQ-9		X ^l	X	X	X	X	X	X	
GAD-7		X ^l		X		X		X	
SAWB ^o			X-----X						
Ongoing Participant Review									
Concomitant therapy									Continuous
Adverse events									Continuous

Footnotes:

- a) The procedures scheduled during the screening visit may be divided over multiple days, according to operational and/or site/country-specific needs. A \pm 1 day window will be allowed for study days 8, 15, 22, 29, 36 and 43.
- b) Must be signed before first study-related activity.
- c) The use of the digital health assessment app is mandatory.
- d) Performed for women of childbearing potential (WOCBP). Serum (β -hCG) pregnancy test performed at Screening. At all other time points, urine pregnancy test will be done. If positive, a serum β -hCG test will be performed. Investigators may perform additional pregnancy testing at their discretion as clinically needed.
- e) 12-lead ECG and vital signs will be taken predose of study intervention.
- f) There are 2 versions of the C-SSRS. A “baseline/screening” version will be conducted at screening. A “since your last visit” version will be conducted predose on visit 2, 3, 4, 5, and 6, at follow-up/early withdrawal.
- g) 12-lead ECG should be performed in triplicate at screening.
- h) If a participant discontinues study intervention before the end of the double-blind phase, early withdrawal (EW) visit should be completed.
- i) Study intervention will be taken at home in the morning at approximately the same time (\pm 4 hours) each day, 30 minutes after the start of breakfast (maximum of 2 hours after the start of breakfast). Recommended to take each dose of study intervention with a glass of water.
- j) On study visits 3, 4, 5, and 6, study intervention will be administered at the study site. The participants are instructed to eat at home and come to the site within an hour or less after completion of the meal. Inability to comply with these instructions would not constitute a protocol violation but the patients are encouraged to comply with these instructions. Dosing should be witnessed by the study staff when study intervention is taken at the study site.

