- v) On Day 1, the baseline hormone sample should be collected before dosing (predose). At all visits, hormone samples should be collected in the morning (7AM-11AM local time).
- w) On Day 1, C-SSRS and YMRS have to be performed pre-randomization to verify eligibility of the participant.
- x) These research samples (TruCulture) will be collected only at certain sites and collected only for sites in the US, Canada, Spain, and Poland.
- y) This research sample (PBMC) may be collected only at certain sites and collected only for sites in the US.
- aa) The general pharmacogenomics sample will be optional and, if not feasible on Day 1, can be collected on any day of the double-blind treatment phase.
- ab) At screening: a urine sample will be analysed by the central lab. All other visits: a dipstick test and only in case of a positive result the urine sample will be analysed by the central lab for confirmation of the positive result.
- ac) In the case of a non confirmatory serology result for Hepatitis B, C and/or HIV, a confirmatory PCR test may be done. Decisions regarding eligibility will be made by the investigator in consultation with the medical monitor on a case by case basis.
- ad) Mood Stabilizer and Antipsychotic Eligibility Assessment form to be completed for patients on a stable adjunctive regimen of an antipsychotic and mood stabilizer.

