11. Has a current or recent (within the past 3 months) history of clinically significant suicidal ideation (corresponding to a score of ≥ 3 for ideation on the C-SSRS) or any suicidal behavior within the last 6 months, as validated on the C-SSRS at screening. Participants with a prior suicide attempt, or history of prior serious suicidal ideation/plan should be carefully screened for current suicidal ideation and only included at the discretion of the investigator.
12. Participant is currently in need of hospitalization.
13. History of malignancy within 5 years before screening (exceptions are squamous and basal cell carcinomas of the skin and carcinoma in situ of the cervix, or malignancy that in the opinion of the investigator is considered cured with minimal risk of recurrence).
14. Known allergies, hypersensitivity, or intolerance to JNJ-55308942, placebo, or its excipients.
15. Had major surgery (e.g., involving a major body cavity or significant blood loss) within 12 weeks before screening, or will not have fully recovered from surgery, or has surgery planned during the time the participant is expected to participate in the study.

Note: Participants with planned surgical procedures to be conducted under local anesthesia may participate.

16. Evidence of clinically severe or active disease, or a clinical finding that is unstable or that, in the opinion of the investigator, would be negatively affected by the study intervention or that would affect the study intervention.

Prior/Concomitant Therapy

17. Taken any disallowed therapies (as noted in Section 6.7, Concomitant Therapy) within the past 4 weeks (5 weeks for fluoxetine) prior to screening.
18. Criterion modified per Amendment 4:
 - 18.1. Newly initiated psychotherapy (defined as psychotherapy that was started within 4 weeks of the screening visit and assessed with the ATHF-SF at screening).

Prior/Concurrent Clinical Study Experience

19. Received an investigational intervention (including investigational vaccines) or used an invasive investigational medical device within 60 days or 5 half-lives, whichever is longer, before the planned first dose of study intervention.
20. Is pregnant, or breast-feeding, or planning to become pregnant while enrolled in this study or within 1 month after the last dose of study intervention.

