5.1.2. Visit Windows

As participants do not always adhere to the protocol visit schedule, the following rules are applied to assign actual visits to analysis visits. Listed below are the visit windows and the target days for each visit. The reference day is Study Day 1 (which is the first day the study drug was taken in the double-blind treatment phase). If a subject has 2 or more actual visits in one visit window, the visit closest to the target day will be used as the protocol visit for that visit window. The other additional

visit(s) will not be used in the summaries or analyses. If 2 actual visits are equidistant from the target day within a visit window, the later visit is used.

All assignments will be made in chronological order. Once a visit date is assigned to a visit window, it will no longer be used for a later time point except for the endpoint. Listed below (Table 2) are the analysis visit windows and the target days for each visit defined in the protocol.

The baseline is defined as the last observation before the start of the first study intervention administration in the double-blind treatment phase. Assessments prior to Day 1 of the double-blind treatment phase that are not considered baseline assessments will be labeled as 'Screening'.

Table 2: Visit Windows

			Time Interval		
	Analysis	Scheduled	(Label on	Time Interval	Target Time
Parameter	Phase	Visit Number	Output)	(Day)*	Point (Day)*
MADRS,	Double-Blind	2	Baseline	≤1	1
CGI-S		3	Week 1	[2,11]	8
		4	Week 2	[12,21]	15
		5	Week 4	[22,35]	29
		6	Week 6	≥36	43
SHAPS	Double-Blind	2	Baseline	≤1	1
		6	Week 6	≥2	43
PROMIS, PHQ-9	Double-Blind	2	Baseline	≤1	1
, ,		3	Week 1	[2,11]	8
		4	Week 2	[12,18]	15
			Week 3	[19,25]	22
		5	Week 4	[26,32]	29
			Week 5	[33,39]	36
		6	Week 6	≥40	43
GAD-7	Double-Blind	2	Baseline	≤1	1
		4	Week 2	[2,21]	15
		5	Week 4	[22,35]	29
		6	Week 6	≥36	43
Clinical	Screening	1	Screening	<1	<1
Laboratory tests	Double-Blind	2	Baseline	≤1	1
(Hematology,		4	Week 2	[2,21]	15
Serum, Urinalysis)		5	Week 4	[22,35]	29
		6	Week 6	[36, Day of FU/EW)	43
		7	FU/EW		49 to 56
Vital signs,	Screening	1	Screening	<1	<1
12-lead ECG,	Double-Blind	2	Baseline	≤1	1
C-SSRS,		3	Week 1	[2,11]	8
Urine Drug Screen		4	Week 2	[12,21]	15
		5	Week 4	[22,35]	29
		6	Week 6	[36, Day of FU/EW)	43
		7	FU/EW		49 to 56
Physical	Screening	1	Screening	<1	<1
examination,	Double-Blind	2	Baseline	≤1	1
Body weight		6	Week 6	[2, Day of FU/EW)	43
		7	FU/EW		49 to 56
YMRS	Screening	1	Screening	<1	<1

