5.6.3.4.2. Columbia Suicide Severity Rating Scale (C-SSRS)

The C-SSRS is a low-burden measure of the spectrum of suicidal ideation and behavior that was developed to assess severity and track suicidal events through any intervention (Posner 2007). It is a clinical interview providing a summary of both suicidal ideation and behavior that can be

administered during any evaluation or risk assessment to identify the level and type of suicidality present. The C-SSRS has been used frequently in clinical studies and is a validated, standard measure for suicidal ideation assessment. Using the C-SSRS, the outcomes will be categorized using the scoring for the 11 categories:

Suicid	Suicidal Ideation (1-5)		
1	Wish to be dead		
2	Non-specific active suicidal thoughts		
3	Active suicidal ideation with any methods (not plan) without intent to act		
4	Active suicidal ideation with some intent to act, without specific plan		
5	Active suicidal ideation with specific plan and intent		
Suicid	Suicidal Behavior (6-10)		
6	Preparatory acts or behavior		
7	Aborted attempt		
8	Interrupted attempt		
9	Actual attempt		
10	Suicide		
Non-s	Non-suicidal self-injurious behavior (11)		
11	Non-suicidal self-injurious behavior		

If no events qualify for a score of 1 to 10, a score of 0 will be assigned (0 = "no suicidal ideation or behavior that can be assessed on the basis of C-SSRS"). A participant with a score of 11 will be considered as not having suicidal ideation or behavior.

Shifts from baseline to the maximum postbaseline score pertaining to suicidal ideation or suicidal behavior (i.e., scores 1 to 10) will be summarized by intervention group.

The maximum score (of scores 1 to 10) assigned to each participant will be grouped into one of three broad categories: No suicidal ideation or behavior (0), Suicidal ideation (1-5), and Suicidal behavior (6-10). Shifts from baseline to the maximum postbaseline category will be summarized by intervention group.

Frequency distribution of the scores for the 11 categories will be provided at each time point by intervention group.

A listing of C-SSRS items throughout the study for participants with Suicidal Ideation or Behavior at any time point will be provided.

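### The C-SSRS shift tables start from the Day 1 since-last-visit form, so low-level ideation recorded at screening that returns after a clear Day 1 is tabulated as a shift from none to ideation

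*SAP*

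**What the plan says.** SAP 5.1.2 sets one baseline rule for all parameters: "The baseline is defined as the last observation before the start of the first study intervention administration in the double-blind treatment phase". Earlier records are kept apart: "Assessments prior to Day 1 of the double-blind treatment phase that are not considered baseline assessments will be labeled as" screening. Table 2 of the SAP accordingly gives the C-SSRS a Screening row and a separate Baseline row with target Day 1.

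The protocol uses two forms of the scale. By footnote f of the Schedule of Activities, the baseline/screening "version will be conducted at screening", while the since-last-visit "version will be conducted predose on visit 2, 3, 4, 5, and 6" and again at follow-up or early withdrawal. Footnote w fixes the Day 1 timing: "On Day 1, C-SSRS and YMRS have to be performed pre-randomization to verify eligibility of the participant".

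SAP 5.6.3.4.2 then reports "Shifts from baseline to the maximum postbaseline score pertaining to suicidal ideation or suicidal behavior" (scores 1 to 10, with 0 assigned when nothing qualifies). A second shift table uses three categories: none (0), ideation (1 to 5) and behavior (6 to 10). The same section plans category frequencies at each time point by arm, and a listing for anyone with ideation or behavior at any time point. Neither that section nor SAP Appendix 2 gives the C-SSRS its own baseline definition.

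**The concern.** A shift table is meant to separate what appeared on treatment from what was already there. Here the form that asks about recent history is left out of the pre-treatment side. The form used in its place looks back only to the screening visit, at most four weeks. The post-treatment side is a maximum over five scheduled forms (Visits 3 to 6 and follow-up), out to Days 49 to 56.

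Eligibility does not remove the problem. Exclusion 11 in protocol section 5.2 rejects anyone who "Has a current or recent (within the past 3 months) history of clinically significant suicidal ideation", defined there as an ideation score of 3 or more, and anyone with suicidal behavior in the past 6 months. Recent ideation of score 1 or 2 can enter. For such a participant a quiet interval before Day 1 sets the tabulated baseline to 0, and a later return looks like a first appearance. At stake is how the emergent-ideation counts in each arm are read. C-SSRS is a named secondary safety endpoint.

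**Working it through.** The plan states no figure on this point, so the check traces the rules.

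**Which form is the baseline**

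1. Baseline is the last observation before first dose (SAP 5.1.2).
2. The Day 1 C-SSRS is taken before randomization (footnote w), so when present it is that last observation.
3. The Day 1 form is the since-last-visit version (footnote f). Screening falls 28 days to 1 day before treatment (protocol 4.1), so it covers 1 to 28 days.
4. The screening form is therefore labelled screening and does not enter either shift table.
5. If the Day 1 form is missing or taken after dosing, the same rule makes the screening form the baseline. Baselines could then mix two recall periods. Appendix 2 accepts postdose Day 1 values as baseline for the patient-reported scales and the YMRS, but does not mention the C-SSRS.

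**Worked cases** (screening = recent-history score; worst predose = higher of screening and Day 1)

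| Case | Screening | Day 1 | Max post | Score shift, SAP | Score shift, worst predose | Category shift, SAP | Category shift, worst predose |
|---|---|---|---|---|---|---|---|
| A, recurrence | 2 | 0 | 2 | 0 to 2 | 2 to 2 | none to ideation | no shift |
| B, persistence | 2 | 2 | 2 | 2 to 2 | 2 to 2 | no shift | no shift |
| C, worsening | 1 | 0 | 4 | 0 to 4 | 1 to 4 | none to ideation | no shift |
| D, behavior | 2 | 0 | 7 | 0 to 7 | 2 to 7 | none to behavior | ideation to behavior |
| E, no return | 2 | 0 | 0 | 0 to 0 | 2 to 0 | no shift | ideation to none |
| F, new onset | 0 | 0 | 2 | 0 to 2 | 0 to 2 | none to ideation | none to ideation |

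Under the SAP, A and F are indistinguishable in both tables. B shows that the problem arises only when Day 1 scores below screening. D shows that serious events register under either baseline: when screening and Day 1 scores are both 0 to 2, any post-baseline score of 3 to 10 is an upward score shift. C shows that the worst-predose baseline, used alone in the category table, would hide a move from 1 to 4. E shows that it also creates downward shifts.

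**Illustration of direction only.** The documents give no rate of ideation. Assume a weekly probability h of 3% or 5%, independent weeks, no drug effect, 2 weeks from screening to Day 1, a 13-week look-back at screening and 8 weeks after Day 1.

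- None to ideation, Day 1 baseline: (1−h)^2 × [1−(1−h)^8]. h = 3%: 0.941 × 0.216 = 0.203. h = 5%: 0.9025 × 0.337 = 0.304.
- None to ideation, worst-predose baseline: (1−h)^15 × [1−(1−h)^8]. h = 3%: 0.633 × 0.216 = 0.137. h = 5%: 0.463 × 0.337 = 0.156.
- Ideation to none, worst-predose baseline: [1−(1−h)^15] × (1−h)^8. h = 3%: 0.367 × 0.784 = 0.287. h = 5%: 0.537 × 0.663 = 0.356.

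The first two lines show recurrence inflating apparent emergence. The third shows the price of a 15-week look-back set against 8 weeks of follow-up. If ideation persists through the screening interval, Day 1 records it (case B) and the gap between the first two lines shrinks.

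**The case against.** The case for leaving the SAP alone has real substance.

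- A reader might infer that screening ideation is discarded. It is not. Table 2 has a Screening row, the frequencies are by time point, and the listing covers the whole study. This stands, but only in part: the frequencies are marginal counts that cannot link one person's screening score to a later one, and the listing is not a by-arm summary.
- A reader might take the shift tables as the trial's principal by-arm account of emergent suicidality. The SAP does not rank its outputs, and adverse event tables are also given by arm.
- The Day 1 baseline compares the same form before and after dosing and errs toward over-counting emergence, which can be defended as cautious for safety.
- Replacing the baseline outright in both tables would do harm: case C loses its category shift, and the longer look-back makes both arms appear to improve. This stands, and it determines the shape of the fix.
- The rule is the same in both arms of a randomized, blinded trial. A reader might infer that it favors one arm; nothing in the documents supports that.

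**Conclusion.** The point holds as a minor matter of definition. As written, both shift tables normally start from a form covering 1 to 28 days, and they cannot separate the return of ideation recorded at screening from first onset. Because Exclusion 11 caps recent history at scores 1 and 2, the effect is mainly on shifts into those scores; shifts to 3 or above are counted as upward in the score table either way. The mixing follows the same rule in both arms and touches no efficacy result.

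How many participants are affected cannot be computed. It is tempting to quote the illustrative 20% to 30% against 14% to 16% as the expected inflation. The documents do not support that, because the weekly rate, the independence between weeks and the 2-week gap are all assumed. The conclusion rests on the written rules alone, with the Day 1 form completed before dosing as scheduled.

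**What to change.** In SAP 5.6.3.4.2:

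1. Define the baseline for the score-level shift table as the higher of the Day 1 score and the screening recent-history score. Use the Exclusion 11 periods: 3 months for ideation and 6 months for behavior, not lifetime. For a correctly enrolled participant the behavior part adds nothing, but stating it completes the definition.
2. Present the category shift table twice, once with the Day 1 baseline and once with the worst-predose baseline, so that worsening inside the 1 to 5 category is not hidden.
3. Footnote both outputs to say that the worst-predose baseline has longer recall than the post-baseline forms, and that downward shifts are not evidence of improvement.

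The cost is a few sentences, one extra table and a C-SSRS-specific exception to the general baseline rule. There is no new data collection, since Exclusion 11 already requires these periods to be assessed with the C-SSRS at screening. The documents do not show the form's fields, so the team should confirm that the recent-history scores are stored separately from lifetime scores.

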5.7. Other Analyses

5.7.1. Pharmacokinetics

PK analyses will be performed on the PK analysis set, defined as participants who have received at least 1 dose of JNJ-55308942 and have at least 1 valid blood sample drawn for PK analysis.

Based on the individual plasma concentration-time data, using the binned nominal sampling times at Visits 2, 3, 4, 5, and 6, descriptive statistics (N, arithmetic mean, SD, coefficient of variation, geometric mean, median, range) will be used to summarize JNJ-553098942 plasma concentrations. All concentrations below the lowest quantifiable (BLQ) concentration will be treated as zero in the summary statistics. Mean and/or median (+/- SD) plasma concentration-time profiles of JNJ-55308942 will be plotted.

5.8. Interim Analyses

No interim analysis is planned.

6. SUPPORTING DOCUMENTATION

6.1. Appendix 1 List of Abbreviations

AE adverse event

ALT alanine aminotransferase
ANCOVA analysis of covariance
AST aspartate aminotransferase
ATC anatomic and therapeutic class

BMI body mass index BD bipolar disorders

CGI-S Clinical Global Impression – Severity

CI confidence interval CRF case report form CSR Clinical Study Report

C-SSRS Columbia Suicide Severity Rating Scale

DSM-5 Diagnostic and Statistical Manual of Mental Disorders-Fifth Edition

ECG electrocardiogram

GAD-7 Generalized Anxiety Disorder – 7 Items

GoF Gain of Function

HDRS-17 Hamilton Depression Rating Scale – 17 Items

HR heart rate

iARBM Integrated Analytical Risk-Based Monitoring

IWRS interactive web response system

LoF Loss of Function

MADRS Montgomery-Asberg Depression Rating Scale

MAR missing at random

MCMC Markov Chain Monte Carlo MDE major depressive episode

MedDRA Medical Dictionary for Regulatory Activities
MINI MINI International Neuropsychiatric Interview
MMRM mixed-effects model for repeated measures

MNAR missing not at random mRNA messenger ribonucleic acid pharmacodynamic(s)

PHQ-9 Patient Health Questionnaire – 9 Item

PK pharmacokinetic(s)

PROMIS Patient-Reported Outcomes Measurement Information System

QTcB QT interval corrected using Bazett's formula QTcF QT interval corrected using Fridericia's formula

QTL Quality Tolerance Limit
SAE serious adverse event
SAP Statistical Analysis Plan
SAWB Self-Assessment of Well-Being

SD standard deviation

SHAPS Snaith-Hamilton Pleasure Scale SNP single nucleotide polymorphism TEAE treatment-emergent adverse event

ULN upper limit of normal VAS Visual Analog Scale

WHO-DD World Health Organization Drug Dictionary

YMRS Young Mania Rating Scale

6.2. Appendix 2 Changes to Protocol-Planned Analyses

Protocol Planned Analysis	Changes and Rationale
Analysis for the following secondary objective: To evaluate the efficacy of JNJ-55308942 compared to placebo on symptoms of depression in a subgroup of patients with messenger ribonucleic acid (mRNA) transcript levels at baseline that exceed the median level for both P2RX7 and IL-1β.	This analysis may be conducted in the future when validated assays for mRNA transcript levels of P2RX7 and IL-1β become available. If conducted, the analysis may be reported separately.
Analyses of the patient-reported outcomes including SHAPS, PROMIS – Ability to Participate in Social Roles and Activities, PHQ-9, and GAD-7; analysis of the safety scale YMRS.	Several participants had their Treatment Day 1 assessment of these scales performed postdose instead of predose as per protocol. The assessments performed postdose on Treatment Day 1 will be included in the analyses as the baseline for these participants.

6.3. Appendix 3 Demographics and Baseline Characteristics

The number of participants in each analysis set will be summarized and listed by intervention group, and overall. In addition, the distribution of participants by country and site ID will be presented unless otherwise noted.

Table 7 presents a list of the demographic variables that will be summarized by intervention group and overall for the safety and the full analysis sets.

Table 7: Demographic Variables

Continuous Variables	Summary Type
Age (years)	Descriptive statistics (N, mean,
Weight (kg)	standard deviation [SD], median,
Height (cm)	and range [minimum and
Body Mass Index (BMI) (kg/m ²)	maximum]).
Categorical Variables	
Age (18-25 years, 26-50 years, 51-64 years)	
Sex (male, female, undifferentiated)	Frequency distribution with the
Race ^a (American Indian or Alaska Native, Asian, Black or African	number and percentage of
American, Native Hawaiian or other Pacific Islander, White, Multiple)	participants in each category.
Ethnicity (Hispanic or Latino, not Hispanic or Latino)	
Country	

^aIf multiple race categories are indicated, the Race is recorded as 'Multiple'

Additional summaries will be presented by the randomization stratification factors (BD type [I or II], country, P2RX7 GoF SNP mutation genotype [homozygous or heterozygous], as well as concomitant medication status [no mood stabilizer or antipsychotic, a mood stabilizer alone, an antipsychotic alone, or a combination of a mood stabilizer and an antipsychotic]) for the full analysis set.

Table 8 presents a list of the baseline disease characteristics variables that will be summarized by intervention group and overall for the safety and the full analysis set.

Table 8: Baseline Disease Characteristics

Continuous Variables	Summary Type
Baseline HDRS-17 total score	Descriptive statistics (N, mean,
Baseline MADRS total score	standard deviation [SD], median,
	and range [minimum and
Baseline CGI-S score	maximum]).
Categorical Variables	
Number of prior nonresponse in the current episode (0, 1, 2, 3, 4)	
BD Type (I or II)	
Baseline CGI-S score (0, 1, 2, 3, 4, 5, 6, 7)	Frequency distribution with the
P2RX7 GoF SNP mutation genotype (homozygous or heterozygous)	number and percentage of
Specific biomarker profile (Yes, No)	participants in each category.
Concomitant medication status (no mood stabilizer or antipsychotic, a	
mood stabilizer alone, an antipsychotic alone, a combination of a mood	
stabilizer and an antipsychotic)	

